The following outcomes will be measured in the baseline and follow-up periods. The baseline period will include claims occurring on the index date, except for the index medication claims, which will be included in the follow-up period.

- All-cause health care resource utilization: Indicator variables and counts of physician office visits, hospital outpatient visits, ED visits, "other" (non-inpatient) visits, inpatient stays, and pharmacy claims will be created. Other medical visits are a residual category that includes, but is not limited to, services rendered at independent laboratories, assisted living facilities, and by home health providers. An indicator variable will be created to identify inpatient stays with an acute stay during the inpatient stay, the time to first inpatient stay will also be captured. The time to first inpatient stay, the time to first eD visit during follow-up will be captured.
- COPD and/or pneumonia-related health care resource utilization: This utilization will be calculated analogously to all-cause utilization, but restricted to medical claims with a diagnosis for COPD and/or pneumonia, in any position (Appendix 1) and pharmacy claims for a COPD-related treatment (Appendix 2), including COPD-guideline recommended antibiotics (Appendix 3).

- COPD-related health care resource utilization: This utilization will be calculated analogously to all-cause utilization, but restricted to medical claims with a diagnosis for COPD in any position (Appendix 1) and pharmacy claims for a COPD-related treatment (Appendix 2), including COPD-guideline recommended antibiotics (Appendix 3)
- Pneumonia-related health care resource utilization: This utilization will be calculated analogously to all-cause utilization but restricted to medical claims with a diagnosis for pneumonia in any position (Appendix 1).
- COPD or pneumonia-attributable health care resource utilization: This utilization will be calculated analogously to all-cause utilization, but restricted to medical claims with a diagnosis for COPD or pneumonia in the primary position or a diagnosis for acute respiratory failure in the primary position and a diagnosis for COPD or pneumonia in a non-primary position (Appendix 1) and pharmacy claims for a COPD-related treatment (Appendix 2), including COPD-guideline recommended antibiotics (Appendix 3)

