- All-cause health care costs (insurer + patient paid amounts): Health care costs will be computed from the payer and patient perspective together. This is the actual amount paid to the provider by the health plan plus the patient co-pay and/or coinsurance amounts, rather than an estimated cost. Total costs will be calculated and presented as the combined pharmacy costs and medical costs. Medical costs will be presented and will include sub-categories of physician office costs, hospital outpatient costs, emergency services costs, inpatient costs, and other costs.
 - Costs will be adjusted to 2019 dollars using the medical care component of the Consumer Price Index (CPI) to reflect inflation between the date of the claim and 2019.²² The final report will include additional columns with the latest available 2020 mid-year CPI adjustment applied to costs for scaling the results as needed.²²
 - Costs from other payers may be important, particularly for studies involving older patients dually eligible for commercial and Medicare coverage. In consultation with this study will NOT incorporate the amounts estimated to be paid by other payers for a total paid or allowable amount.²³
- COPD and/or pneumonia-related health care costs (insurer + patient paid amounts): These costs will be calculated analogously to the all-cause costs, but restricted to medical diagnosis claims with а for COPD. pneumonia, or acute bronchitis/bronchiolitis in any position (Appendix 1) and pharmacy claims for a COPDrelated treatment (Appendix 2), including COPD-guideline recommended antibiotics (Appendix 3).
- COPD-related health care costs (insurer + patient paid amounts): These costs will be calculated analogously to the all-cause costs, but restricted to medical claims with a diagnosis for COPD in any position (Appendix 1) and pharmacy claims for a COPD-related treatment (Appendix 2), including COPD-guideline recommended antibiotics (Appendix 3).

Proprietary confidential information © 2022 Boehringer Ingelheim International GmbH or one or more of its affiliated companies

- Pneumonia-related health care costs (insurer + patient paid amounts): These costs will be calculated analogously to the all-cause costs but restricted to medical claims with a diagnosis for pneumonia in any position (Appendix 1).

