- COPD or pneumonia-attributable health care costs (insurer + patient paid amounts): These costs will be calculated analogously to the all-cause costs, but restricted to medical claims with a diagnosis for COPD or pneumonia in the primary position or a diagnosis for acute respiratory failure in the primary position and a diagnosis for COPD or pneumonia in a non-primary position (Appendix 1) or pharmacy claims for a COPDrelated treatment (Appendix 2), including COPD-guideline recommended antibiotics (Appendix 3).

Clinical characteristics will be measured in the baseline period. The baseline period will include claims occurring on the index date, except for the index medication claims, which will be included in the follow-up period.

- Quan-Charlson comorbidity score: A comorbidity score will be calculated based on the presence of diagnosis codes (in any position) on medical claims in the baseline period. 24.25.26 The score is calculated based on a weighted sum of 12 comorbid conditions. The score represents the cumulative likelihood of one-year mortality and serves as a proxy for comorbidity burden. The Quan-Charlson comorbidity score also will be categorized into the following groups: zero, one, two, three, four, and five or more.
- Oxygen therapy: Evidence of oxygen use will be captured in the baseline period based on diagnosis (ICD-9, ICD-10), procedure (HCPCS, CPT, ICD-9) and revenue codes for oxygen therapy (Appendix 1).

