9.3.2.2 Secondary Outcome(s)

The secondary outcome is time to first hospitalization for community-acquired pneumonia (serious pneumonia). Pneumonia was defined using ICD-9-CM diagnoses 481.x-486.x; 487.0, 507.x, 507.0, 507.1, 507.8, 510.0, 510.9, 511.0, 513.0, 514.x, 517.1, 519.8, 530.84, and ICD-10 diagnosis codes J10.0; J11.0; J12-J18; J22; J69; J85.0; J85.1; J86. This definition has been previously used in COPD. ^{27,28}

- COPD and/or pneumonia related HCRU (including acute inpatient stays and their length of stay, emergency department visits, ambulatory [Physician office visits, hospital outpatient visits], and other medical visits)
- COPD-related HCRU
- Pneumonia-related HCRU
- COPD-attributable HCRU
- All-cause HCRU

HCRU is defined as total inpatient, emergency department, and outpatient care episodes. Estimates will be presented both overall and for COPD and/or pneumonia-related care, defined as claims where a diagnosis of COPD or pneumonia is present. Medications used, defined as total number of distinct medication subclasses dispensed (e.g., 4-digit level of the Generic Product Identifier) and total number of dispensing for medications per year. COPDrelated medication utilization included all COPD medications, OCS, and guidelinerecommended antibiotics

Annual HCRU costs (including costs paid by the patient, health plan, and any third party via coordination of benefits) will be then calculated as total costs, medical costs, pharmacy costs, ambulatory costs, ED costs, inpatient costs, and other costs. Costs were defined as related to COPD if the claim has a diagnosis for COPD in any position or is a pharmacy claim for a medication used to treat COPD. The sum of all costs from all care settings and pharmacy dispensing will be assessed overall, for COPD and/or pneumonia-related care.

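### Antibiotic and OCS fills for pneumonia are counted as COPD-related and never as pneumonia-related, and COPD-attributable HCRU has no COPD-only definition

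*Combined protocol and SAP*

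**What the plan says.** Section 9.3 assigns medical claims to a disease by diagnosis code. COPD-related HCRU is "restricted to medical claims with a diagnosis for COPD in any position", plus pharmacy claims for any Appendix 2 drug, "including COPD-guideline recommended antibiotics" from Appendix 3. Appendix 2 lists OCS among the rescue medications. Appendix 3 contains general-use agents such as amoxicillin, doxycycline and sulfamethoxazole/trimethoprim. COPD-related costs follow the same rule. Section 9.3.2.2 agrees: "COPDrelated medication utilization included all COPD medications, OCS, and guidelinerecommended antibiotics".

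The pneumonia counterparts have no pharmacy element. Pneumonia-related HCRU is "calculated analogously to all-cause utilization but restricted to medical claims with a diagnosis for pneumonia in any position", and pneumonia-related cost is "calculated analogously to the all-cause costs but restricted to medical claims with a diagnosis for pneumonia in any position".

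For attributable measures, Section 9.3 defines only "COPD or pneumonia-attributable health care resource utilization" and "COPD or pneumonia-attributable health care costs". Both require a primary-position diagnosis of COPD or pneumonia, or acute respiratory failure in primary position with either disease in a non-primary position. Both then add the same unlinked Appendix 2 and 3 fills. The outcome list in Section 9.3.2.2 names "COPD-attributable HCRU", with no definition of its own.

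**The concern.** A medical claim must carry the relevant code to be counted for a disease. An antibiotic or OCS fill need not. It becomes COPD-related whatever it was dispensed for, and it also enters the attributable measure, where the rule for visits is strict.

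This matters because the study rests on a trade-off between exacerbations and pneumonia. Section 7 expects 53% greater pneumonia risk on triple therapy than on dual bronchodilation. If more Trelegy patients are treated for pneumonia, the rule adds more of those fills to Trelegy's COPD-related pharmacy use and cost. The pneumonia-related figures, which a reader would consult for the pneumonia burden, omit the drugs in both cohorts. Section 9.3.2.2 lists COPD-related and pneumonia-related HCRU as separate outcomes, so the split will be reported and interpreted.

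The undefined attributable outcome is a gap of another kind. Whoever programs it must choose a rule that the plan does not give.

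**Working it through.** The plan states no figure on this point, so there is none to reproduce. The check compares the definitions and then sizes the effect on stated assumptions.

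**Definitions compared**

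| Measure | Medical claims | Antibiotic and OCS fills |
|---|---|---|
| COPD-related HCRU, cost | COPD code, any position | all listed fills, no link |
| Pneumonia-related HCRU, cost | pneumonia code, any position | none |
| Pooled related HCRU, cost | includes COPD or pneumonia code, any position | all listed fills, no link |
| Pooled attributable HCRU, cost | primary-position rule, either disease | all listed fills, no link |
| COPD-attributable HCRU (9.3.2.2) | not defined | not defined |

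Three consequences follow:

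- An antibiotic dispensed for coded pneumonia is COPD-related and never pneumonia-related. The pneumonia drug component is zero by construction.
- Moving a fill between COPD and pneumonia leaves the pooled related total and the all-cause total unchanged. Only fills unrelated to either disease distort the pooled measure.
- The plan can link fills to visits. In Section 9.3 a moderate exacerbation needs an office or outpatient visit with a COPD code within ±7 days of the fill. That link is not used for HCRU or cost.

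**Share of COPD-related pharmacy claims unrelated to COPD**

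Assumptions, not in the documents: 0.3 to 0.6 listed antibiotic fills per patient-year for non-COPD reasons, and 8 to 12 COPD-related fills per patient-year.

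- Lowest: 0.3 / 12 = 2.5%.
- Highest: 0.6 / 8 = 7.5%.

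This share arises in both cohorts. It dilutes the measure but is not in itself a difference between arms.

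**Between-arm shift from pneumonia treatment**

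Inputs: pneumonia in 14.5% (tiotropium + olodaterol) and 19.3% (triple therapy) in the second study described in Section 9.5, and 3018 matched patients per cohort (Section 9.5). Assumption: 1 to 2 outpatient antibiotic or OCS fills per patient with pneumonia.

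- Difference in proportions: 0.193 − 0.145 = 0.048.
- Extra fills per patient on triple therapy: 0.048 × 1 = 0.048 to 0.048 × 2 = 0.096, about 0.05 to 0.10.
- Per cohort: 3018 × 0.048 ≈ 145 to 3018 × 0.096 ≈ 290 fills.
- Relative to assumed COPD-related fills: 0.048 / 12 = 0.4% to 0.096 / 8 = 1.2%.

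With a wider assumption of 0.5 to 3 fills per pneumonia patient, the shift is 0.024 to 0.144 fills per patient, or about 72 to 435 fills per cohort.

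**The case against.** The strongest reply is that the secondary objective in Section 8 does not ask for COPD and pneumonia to be separated. It names all-cause and pooled COPD and/or pneumonia-related HCRU and cost. Misallocation between the two diseases cannot alter the first and cancels in the second. Section 9.7.1 presents HCRU descriptively, and Section 9.7 says only that annualised cost may be modelled. This stands. A reader might infer that the HCRU objective fails, and the documents do not support that. What remains is that the separate breakdowns are listed outcomes and follow a rule that misplaces pneumonia drugs.

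A reader might also infer that pneumonia-primary admissions will be reported as COPD-attributable. The plan does not say so. An analyst could report the pooled measure under its own open name, or use only its COPD part. Pneumonia belongs in the pooled attributable measure by design. The supportable statement is that the COPD-attributable outcome is undefined.

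Third, leaving fills unlinked is a disclosed choice. Section 9.9 concedes that indication can only be inferred from diagnostic patterns, and the pneumonia measure is openly limited to medical claims. Linking also has limits. Every patient has COPD and COPD codes count in any position, so a pneumonia visit with a secondary COPD code would link its antibiotic to both diseases. Genuine COPD fills with no nearby coded visit would be lost. These points stand as reasons for a priority rule and for keeping unlinked fills in the main COPD total. They do not justify a pneumonia measure with no drug component.

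**Conclusion.** The point holds, with limited reach. The separate COPD-related and pneumonia-related breakdowns misplace pneumonia drugs, the attributable measures admit fills regardless of reason, and one listed outcome has no definition. The primary time-to-exacerbation outcome and all-cause results are unaffected. The pooled related measure is affected only through fills unrelated to either disease.

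The size is modest: 2.5-7.5% of COPD-related pharmacy claims unrelated to COPD, and a between-arm shift of about 0.05-0.10 fills per patient (about 0.4-1.2%), in the direction of more COPD-related pharmacy use on Trelegy. The fill rates are assumptions. The pneumonia proportions come from a Medicare Advantage Part D population in a different study, and they are set against annual fill counts only as an approximation. No cost effect can be computed from the documents. The change is worth making, but the study's main conclusions do not depend on it. The undefined outcome is the firmer of the two parts, because it needs no assumption.

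**What to change.** In Sections 9.3 and 9.3.2.2:

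1. Add to pneumonia-related HCRU and cost the antibiotic and OCS fills within ±7 days of a pneumonia-coded claim. State a priority rule: in the separate breakdowns, a fill near both a pneumonia and a COPD code goes to pneumonia.
2. Beside the current rule, report COPD-related HCRU and cost with antibiotic and OCS fills limited to those within ±7 days of a COPD-coded visit, as a sensitivity analysis. Show unlinked fills separately.
3. Define COPD-attributable (COPD primary, or acute respiratory failure primary with COPD) and pneumonia-attributable separately, then their union, for both HCRU and cost. Alternatively, delete the undefined item from Section 9.3.2.2.

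The cost is some extra programming, much of it adapted from the exacerbation linkage, and no new data. In the sensitivity analysis, genuine COPD fills without a nearby coded visit drop out, though they stay in the all-cause totals. Medical claims carrying both codes will still count in both related measures, and the report should say so.

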In view of all the above findings which represent a limited view of the patients who could potentially use these FDC TT treatments we intend to conduct an observational study in a real-world clinical practice setting. There is a clear unmet need for better evidence on specific patient populations upon which to base FDC TT treatment recommendations. We propose to assess the effectiveness of Trelegy Ellipta, a FDC TT and compare it with Stiolto, a FDC DBT in patients who are maintenance treatment naïve and measure the incidence of COPD exacerbation, the incidence of community acquired pneumonia, health care resource utilization (HCRU) and associated HCRU costs.

Trelegy Ellipta is a FDC of TT (Fluticasone Furoate + Umeclidinium + Vilanterol, 100/62.5/25 mcg) approved by the FDA in September 2017 for once-daily, maintenance treatment of COPD. Stiolto Respimat is a FDC of DBT (tiotropium bromide + olodaterol, 5/5 mcg), approved by FDA in May 2015 for once-daily, maintenance treatment of COPD).

Proprietary confidential information © 2022 Boehringer Ingelheim International GmbH or one or more of its affiliated companies

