Inclusion Criteria:

- \geq 40 years of age as of the year of the index date
- At least one pharmacy claim for Stiolto Respimat or Trelegy Ellipta between 15 September 2017 and 31st March 2020.
 - For Stiolto Respimat users, the first pharmacy claim of FDC of Tiotropium + Olodaterol (5/5 mcg) will be defined as the index date.
 - For Trelegy Ellipta users, the first pharmacy claim of FDC of Fluticasone Furoate + Umeclidinium + Vilanterol (100/62.5/25 mcg), will be defined as the index date.
- Two medical claims (at least one claim on index date or before in the baseline period) with an ICD-9/10 diagnosis code(s) for COPD in any position during the study period (baseline ± post index date).
- At least one year of continuous medical and pharmacy health plan eligibility prior to the index date is required (to allow a baseline period for the covariates and characterizing the study population).

Exclusion Criteria:

- To increase the likelihood of a true diagnosis of COPD, we will exclude all patients with two medical claims of asthma, cystic fibrosis, lung cancer, or interstitial lung disease in any position on separate dates of service during the study period.
- To restrict the cohort to first line maintenance therapy of Stiolto Respimat or first line maintenance therapy of Trelegy Ellipta we will exclude; patients on LAMA. monotherapy; LABA monotherapy; ICS monotherapy; free or FDC of ICS+LABA, LAMA+LABA, ICS+LABA+LAMA therapy within six months prior to index date.
- Pharmacy claims for multiple index medications on the index date.
- Pharmacy claims for non-index COPD maintenance medications on the index date.

Proprietary confidential information © 2022 Boehringer Ingelheim International GmbH or one or more of its affiliated companies

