 be counted as one test.

Patient characteristics will be measured as of the index date, or the first available claim after the index date with valid values for each of the characteristics. It may be necessary to modify or remove some variables or analytic table templates to preclude identification of individual patients and protect proprietary health plan information.

- Index year: The year of the patient's index date will be identified.
- Seasonality: The month of the patient's index date will be identified and classified as fall (September, October, November), winter (December, January, February), spring (March, April, May), or summer (June, July, August).
- Age: Age will be defined as of the index year
- Age groups: Patients will be assigned to one of the following age groups: 40-44, 45-49, 50-54, 55-59, 60-64, 65-69, 70-74, 75-79 and 80+
- Gender: Gender will be captured from enrolment data; patients with undefined gender will be removed from the study sample
- Race/ethnicity: Race/ethnicity information will be captured if available in the database, no further linking with any additional consumer sociodemographic data will be attempted, but if data is available it will be categorized as follows: White, African American/Black, Asian, Hispanic, or unknown (unknown includes missing). This variable depends on the availability of data and will be missing for some or all patients.
- Insurance type: Whether the patient was covered under a commercial or Medicare Advantage health plan will be captured
- Plan type: Plan type will be categorized as Exclusive Provider Organization (EPO), Health Maintenance Organization (HMO), Point of Service (POS), Preferred Provider Organization (PPO), Individual and Other
- Geographic region: The US region in which the study patient is enrolled in a health plan will be determined and reported and states will be categorized into five geographic regions in accordance with the US Census Bureau's region designations; the four health plan regions are presented in the table 1 below. Patients categorized into "other" will be excluded from the study.

Region	State
Northeast	CT, MA, ME, NH, RI, VT, NJ, NY, PA
Midwest	IL, IN, MI, OH, WI, IA, KS, MN, MO, ND, NE, SD
South	DC, DE, FL, GA, MD, NC, SC, VA, WV, AL, KY, MS, TN, AR, LA, OK, TX
West	AZ, CO, ID, MT, NM, NV, UT, WY, AK, CA, HI, OR, WA

Table 1Health Plan Regions

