9.3.1 Exposures

Patients will be assigned to one of the following mutually exclusive study cohorts based on the index pharmacy claim: Stiolto Respimat or Trelegy Ellipta. Exposure measures will be based on pharmacy dispensing of the two medications under study, namely Stiolto Respimat or Trelegy Ellipta, over a follow-up period, beginning the index date and lasting up to one year from index date. Discontinuation for index medication will be defined as a gap in index medication of \geq 45 days (sensitivity analysis with \geq 30 days can be included) following the runout of days' supply (discontinuation date = runout prior to the gap in therapy). Switch in index medication will be defined as a pharmacy fill for \geq 30 consecutive days of a non-index maintenance medication (switch date = first date of the new treatment regimen). Switch includes any other change in use of index medication by active ingredient, inclusive of a change to a different combination therapy (ICS/LABA FDC, different LAMA/LABA or LAMA/LABA/ICS FDC) change from a FDC to a free form combination therapy with mono LAMA plus mono LABA, or mono ICS plus mono LABA, or mono LAMA plus mono LABA plus mono ICS or a change to a monotherapy.

Individuals in the study cohort will be followed from the index date until the earliest of the date of a switch in treatment, addition of an ICS for the Stiolto Respimat group, discontinuation of the index COPD maintenance treatment, the end of the study period, or the end of continuous health plan eligibility. Main analyses will be further limited to the first 12 months after index date, with sensitivity analyses considering all available data.

All patients will be required to be continuously enrolled in the health plan for a minimum of 12 months. The 12 months prior to and including the index date (index date – 364 through index date) will be used to assess baseline characteristics. The period starting the day after the index date, up to a maximum of 12 months duration (index date +1 through index date +365) will be used to assess exacerbation, pneumonia, HCRU and cost outcomes. Patients will be censored at the earliest of the following: discontinuation of the index medication (Stiolto or Trelegy), switch to a non-index medication, disenrollment from the health plan, 12-months following the index date, or the end of the study period.

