9.3.3 Covariates

Patient characteristics at baseline will be assessed for Stiolto and Trelegy users overall and stratified by history of exacerbation.

The covariates included in the Propensity Score Matching (PSM) will include all the below covariates including the ones defined during the 12-month pre-index baseline period and chronic comorbid conditions.

- Gender
- Age group (years, categorical and a continuous variable)
- Calendar year of cohort entry
- Region
- Insurance type (e.g., Commercial, Medicare)
- Season of index date (winter, spring, summer, fall)

Additional characteristics that will be defined during the 12-month pre-index baseline period:

- Previous acute COPD exacerbation (measured both overall and in the 30 days prior to cohort entry), categorized as 0, 1, or ≥2.
 - All exacerbations (Moderate+Severe)
 - Hospitalizations (Severe)
- Use of other respiratory drugs in the 12-month pre-index period:
 - Short-acting beta-agonists
 - Short-acting Anticholinergics
 - Methylxanthines
 - o LAMA
 - o LABA

Proprietary confidential information © 2022 Boehringer Ingelheim International GmbH or one or more of its affiliated companies

- o ICS
- o ICS/LABA
- Use of antibiotics commonly prescribed for a respiratory condition (e.g., azithromycin)
- Use of OCS
- Oxygen Use
- Pulmonary Rehabilitation

Chronic comorbidities were defined using diagnoses identified during all available data prior to the index date, and included

- Quan-Charlson Comorbidity Index score/individual comorbidities
- Cardiovascular disease
- Diabetes
- Renal failure
- GERD
- Arthritis
- Osteoporosis
- Cancer (excluding basal cell carcinoma)
- Baseline pneumonia diagnosis
- Baseline acute bronchitis diagnosis
- Diagnosis of dyspnea during baseline identified using ICD 9 786.0x and ICD 10 R06.0x
- Diagnosis of obesity during baseline identified using ICD 9 278.xx and ICD 10 E66.xx
- Diagnosis of alcohol dependence during baseline identified using ICD 9 303.xx, 305.0x and ICD 10 F10.xx
- Smoking dependence during baseline identified using ICD 9 305.1 and ICD 10 F17.xx
- Tobacco use or cessation counselling*

*We anticipate limited capture of lifestyle variables known to be risk factors and potential confounders, including obesity, smoking status, and excessive alcohol consumption.

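### Calendar year plus a four-level season treats January-February and December starters of 2018 (and of 2019) as equal in entry time; the likely effect on the overall HR is under 1%, and a quarter or month factor removes it

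*Combined protocol and SAP*

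**What the plan says.** Protocol section 9.3 (Variables) defines two entry-time variables:

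- Year: "Index year: The year of the patient's index date will be identified".
- Season, from the index month: "fall (September, October, November), winter (December, January, February), spring", with spring and summer following in three-month blocks.

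Section 9.3.3 (Covariates) puts both into the propensity score as separate items: "Calendar year of cohort entry" and "Season of index date (winter, spring, summer, fall"). No month, quarter or year-by-season term is listed.

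The index window (section 9.2.2) is "At least one pharmacy claim for Stiolto Respimat or Trelegy Ellipta between 15 September 2017 and 31st March 2020". Outcomes are counted on treatment over "index date +1 through index date +365) will be used to assess exacerbation, pneumonia, HCRU and cost outcomes" (section 9.3.1), with censoring at the end of the study period.

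Section 7 gives the approval dates. Trelegy was "approved by the FDA in September 2017 for once-daily, maintenance treatment of COPD"; Stiolto was "approved by FDA in May 2015 for once-daily, maintenance treatment of COPD".

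Balance is judged by a standardized difference above 10% (sections 9.2.4, 9.7 and 9.7.1). Interaction terms are offered only where a characteristic fails that check.

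**The concern.** Season is in the score because exacerbations and pneumonia vary over the year, and calendar year is there because prescribing drifts. Coded separately, the two do not identify which winter a patient entered. A start on 15 January 2019 and one on 15 December 2019 both read as 2019, winter, and can be matched as equal. The first falls in the 2018-19 respiratory season and the second in 2019-20, with far less possible follow-up.

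This matters only if the arms differ in their December share within the cell. Trelegy was new when the window opened and Stiolto had been on the market for over two years, so a difference is plausible. It would stay hidden: year and season can each show a standardized difference near zero while the December versus January-February split does not, and that split is not on the list to be checked.

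**Working it through.** The plan gives no figure that rests on this coding, so there is nothing to reproduce. The check covers the dates, which cells are mixed, and the size of the bias.

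**Dates (from the documents)**
- 1 January to 31 December of one year is 364 days; 28 February to 1 December is 276 days. By month the gap is 11 and 10 months.
- 15 December 2019 to 31 March 2020: 16 + 31 + 29 + 31 = 107 days. From 15 January 2019 it is 441 days, capped at 365.

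**Which cells are mixed**
- Winter 2017 holds only December and winter 2020 only January-February. Only the 2018 and 2019 winter cells mix the two.
- The window has 108 + 365 + 365 + 91 = 929 days. With flat starts the two mixed cells hold 2 × 90 / 929 = 19% of starts, and December is 31/90 = 34% of each.

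**Would the balance check see it?**
- Under three assumed rising uptake curves for Trelegy, December is 58% to 78% of its 2018 winter cell and 34% to 52% of its 2019 cell.
- Against 34% for a flat Stiolto, the standardized difference within the 2018 cell is (0.58 − 0.34)/√[(0.34×0.66 + 0.58×0.42)/2] = 0.50. At 78% it is 0.99. The check is not applied to this split, so neither would be reported.

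**Bias in the HR**

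The expected Cox score equation was solved with no true drug effect and both arms reweighted to the same totals per time cell. None of the inputs below is in the documents:
- flat Stiolto starts and the three Trelegy uptake curves;
- seasonal peak-to-trough hazard ratio of 1.5 or 2.0;
- 2017-18 winter hazard multiplied by 1.0 or 1.3;
- discontinuation of 0.7 or 2.0 per year;
- baseline hazard of 0.8 per year.

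This gives 3 × 2 × 2 × 2 = 24 scenarios.

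| Time control | Spurious HR, Stiolto vs Trelegy |
|---|---|
| None | 0.969 to 1.027 |
| Plan's year × season cells | 0.992 to 1.001 |
| December moved to next winter | 1.000 to 1.002 |
| Year × month | 1.000 |
| Plan's coding, 2018 winter cell alone | 0.963 to 1.034 |

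The sign depends on how severe the 2017-18 winter was. With multiplier 1.0 the 2018 cell gives 0.963 to 0.993; with 1.3 it gives 1.013 to 1.034. Overall the ranges are 0.992 to 0.999 and 0.997 to 1.001.

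The table assumes joint balance on year and season, which a main-effects score does not guarantee. A second calculation with a main-effects score gave 0.993 to 1.004 for the plan's coding, up to 1.008 with only December recoded, and 1.000 to 1.001 with a quarter or month factor.

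**The case against.** The strongest reply is that this is a preference about covariate granularity. All three months are winter, so season at entry is adjusted for. Only two cells are mixed. The plan's coding already removes most of the time-related distortion (the first two rows of the table). If the 3018 pairs yielded 1,000 to 2,000 first events (an assumption), the standard error of the log HR would be about 2/√events, or 0.063 to 0.045. A log-HR bias of 0.0084 (HR 0.9916) is then 0.13 to 0.19 of a standard error. Section 9.7.1 also admits data-derived variables, so a finer time term is allowed. All of this stands and fixes the rank of the point. It does not remove it, because a finer term is allowed but not promised, and the listed balance checks would not prompt one.

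A reader might go further and infer an established seasonal confounding that runs against Trelegy in both the exacerbation and pneumonia HRs. The documents do not support that. They give no starts by month, so late-year clustering of Trelegy is an inference from two approval dates. The direction changes with the severity of one winter, and pneumonia was not modelled.

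Nor should the hazard contrast over a short window be read as typical. With a hazard varying by ±30% around a 20 January peak, a mid-December starter's mean hazard over 107 days is 1.12 times the average for mid-January and mid-February starters. The 107-day limit binds only in mid-December 2019. Over a full 365 days without dropout the ratio is 1.00; with assumed dropout of 1.5 to 2.8 per year it is 1.05 to 1.08.

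Setting the bias beside the HR of 0.97 quoted in section 9.5 is also unsound. That figure is from a different study, has a 95% CI of 0.87 to 1.08, and is not this study's target effect.

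**Conclusion.** The coding gap is real: the plan cannot tell January-February from December starters of 2018, or of 2019, and its balance table would not show a difference between the arms. The consequence is minor. The bias in the overall HR is under 1% in every scenario run, in either direction, and reaches about 4% only inside the 2018 winter cell. These sizes rest on assumed uptake, seasonality and discontinuation. They cover the exacerbation hazard only and leave out drift in patient mix after launch, which could add to them. It is worth changing because the change costs almost nothing, not because the primary result is in danger.

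**What to change.** In sections 9.3 and 9.3.3, replace the separate year and season terms with one variable: calendar quarter (or month) of index date, Q3 2017 to Q1 2020, entered as a factor in the propensity score. Report its balance before and after matching.

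Do not rely on moving December to the following winter alone; with a main-effects score that left a spurious HR of up to 1.008. Do not require exact matching on quarter. It could lose pairs in the launch quarters, where Trelegy starts may be scarce; the documents give no counts to estimate that loss, and section 9.7 requires at least 2000 matched patients per cohort.

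The cost is recoding one covariate from index dates already held. As a factor in the score it should lose practically no pairs.
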